And what is the cost effectiveness of implementing evidence-based interventions at different doses? This project has the potential to dramatically improve the services families of young children with ASD in Philadelphia receive, and significantly improve long-term outcomes. Successful completion of the proposed study would provide the EI system with the information needed to bring this type of intervention to scale across the entire system. Findings from this pilot trial would serve as the foundation for an application for federal funds to conduct a large-scale, system-wide study of Project ImPACT implemented in all Philadelphia agencies serving infants and toddlers with ASD.

RESEARCH PLAN

The proposed study is highly innovative. Foremost, the choice of intervention, the study questions and the study design all were developed in partnership with leaders from Philadelphia's infant and toddler early intervention system, which increases the ecological validity and utility of the findings, and the potential for the study to lead to lasting changes in Philadelphia's early intervention system. Second, the study comprises a field trial of an intervention for young children with ASD using community (as opposed to university-based) clinicians to train parents in the intervention. This model of testing effectiveness is rare, with similar studies published mostly from data collected outside of the United States. Third, our sample will be culturally and socioeconomically diverse, a limitation of almost all prior autism intervention studies. Fourth, we propose to test two doses of the same intervention. While determining the most effective dose of intervention is of critical importance to the field, there has been no head-to-head comparison in a randomized trial. Fifth, we propose to measure family as well as child outcomes, which rarely have been reported in intervention trials.

Setting for all Research Activities

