Changes in response to COVID-19: The early intervention system is providing all direct service to families via tele-intervention. The research team will not visit families' home for any research activities until local and state authorities indicate that in-home intervention can be resumed. All research activities will be conducted remotely via tele-intervention, shared video recordings, and electronic surveys. Consistent with all services being delivered by the early intervention system, Project ImPACT and treatment as usual will be delivered via tele-intervention. The research team will join tele-intervention sessions for fidelity monitoring and coaching. Direct observation assessments will now be conducted via observations of self-recorded parent-child play interactions. Per these changes, families should have the ability and technology to participate in tele-health sessions with their EI provider in order to participate in the study.

Measures

Child Outcomes (all measures collected at baseline and 6 months):

Changes in Social Communication will be measured using the communication and social domains of the *Vineland Adaptive Behavior Scales–3rd Edition*⁴³ and the *Preschool Language Scales–5th Edition* (PLS). The Vineland is a standardized parent report survey of adaptive functioning that has been normed on individuals ages birth to 90 years. It has excellent psychometric properties

and has been used in many studies of children with autism. Previous research has shown that Communication and Social Domain standard scores are sensitive to change in response to ImPACT. 19,44 The PLS is an interactive direct assessment of developmental language skills that can be given to children birth to seven years. Primary domains include auditory comprehension and expressive communication. It is designed to test a full range of communication skills across the developmental spectrum (including attention, play, gesture, and social communication). It has demonstrated strong reliability and validity across a diverse population, including clinical samples and children with ASD. We will use standard scores on auditory comprehension and expressive communication, as well as total standard scores, in the analyses. A research team member trained to reliability of administration will administer the PLS under the supervision of a licensed psychologist.

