Changes in response to COVID-19: The Vineland will be administered to parents via a secure electronic survey link, instead of in person.

Children's Social Communication will be measured using the *Brief Observation of Social Communication Change (BOSCC)* scoring applied to the parent-child interaction videos, instead of the Preschool Language Scales. The BOSCC is an observational coding scheme designed to be sensitive to changes in social communication behavior, easily used by naïve, minimally trained examiners and coded relatively quickly. The BOSCC has strong interrater and test-retest reliability, sensitivity to change, and evidence of convergent and discriminative validity. The BOSCC scoring procedure will be used to measure child social communication behaviors during a parent-child play interaction. The BOSCC does not require direct contact with the parent or child to administer, so is an appropriate outcome measure to use in response to the COVID-19 pandemic. Parents will self- record a 10-minute play interaction between the parent and child using their phone, tablet, or any personal device and will share the recording with the research team via a secure Penn Medicine ShareFile link. ShareFile is a Citrix program that allows its users to share and receive large files securely.

Parent Outcomes (All measures will be completed at baseline, 3 months, and 6 months)

Parenting Self-Efficacy will be measured using the Early Intervention Parenting Self-Efficacy Scale (EIPSES), ⁴⁵ a 16-item self-report measure that examines parents' beliefs about their ability to produce positive changes and promote optimal development in their child with a disability. It measures two dimensions of self-efficacy: Parent Outcome Expectations and Parent Competence. Parents rate items from 1 ("Strongly disagree") to 7 ("Strongly agree") with higher scores indicative of higher parenting self-efficacy. The EIPSES has strong psychometric properties and been used in a number of studies of families receiving Part C services.

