Following introductory training, clinicians in each agency will participate in bi-weekly group consultation meetings with Penn consultants (see below) via videoconferencing. During these 1-hour group meetings, clinicians will present their Project ImPACT cases to the other clinicians in their agency and receive feedback and problem solving from the Penn consultant. Each clinician also will receive a monthly consultation visit in the field. During these 1-hour sessions, the consultant will observe an intervention session, complete the coaching fidelity form, and provide feedback to the clinician on Project ImPACT implementation. [name] team has successfully used this remote consultation model to train clinicians to fidelity in Project ImPACT with high ratings of satisfaction, self-efficacy, and attendance from clinicians who participated in the training.⁴¹

To prepare Penn staff to consult in the field, [name] and the MSU research team will train them to fidelity in Project ImPACT and its coaching model, and fidelity monitoring. This training will include the same introductory training described above, consultation meetings with MSU study staff to provide feedback on program implementation with a family with ASD via videoconferencing; and obtaining reliability on parent treatment adherence and coaching fidelity scoring for master session tapes. Once Penn staff have been trained to fidelity in coaching and reliability in fidelity monitoring, they will meet biweekly with MSU staff via video-conferencing for supervision as they provide monthly consultation sessions to community clinicians using Project ImPACT. MSU research staff also will conduct twice-a-month cross-site video-based fidelity checks to ensure that Penn staff is providing training and feedback to the clinicians implementing the program in a way that is consistent with the Project ImPACT model.

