Clinician Fidelity will be measured using the Project ImPACT Coaching Fidelity Checklist.¹ Clinicians assigned to the two active treatment groups will self-monitor their coaching fidelity as part of the implementation procedure. We also will observe clinicians monthly to ensure accurate self-monitoring in the active treatment groups and to capture the extent to which clinicians in the treatment as usual group use any elements of ImPACT. Previous research indicates high interrater reliability between self and observer ratings on the coaching fidelity form (99% exact agreement);⁴² thus we anticipate that self-ratings will provide an accurate measure of clinician behavior.

Cluster Randomized Study Design

Six agencies will be blocked into groups of 3 based on agency size and location. Within each group of three, each agency will be randomized to one of three conditions: 1) treatment as usual; 2) ImPACT at a dose of 1 hour/week over 6 months; and 3) ImPACT at 4 hours/week over 6 months.

Statistical Analysis for Aim 1

Outcomes will be analyzed as continuous variables at the child or parent level across time. Initially all outcomes will be described using summary statistics (means, medians, and estimates of variance). The longitudinal nested random effects linear models will be used for each outcome; the models will consist of three levels of random effects to adjust for individual child/parent, agency and clinician variability. For each measure, the analysis dataset will contain one observation with each subject's outcome measure at baseline and follow-up. The dependent variable in each model will be the measure of outcome at each time point. The independent variables will include a categorical variable for time period (baseline, 3 months, or 6 months), group (ImPACT_1hr/wk, ImPACT_4hr/wk or comparison), and their interaction. The magnitude and statistical significance of the beta coefficient for the interaction will provide an intent-to-treat assessment of the extent to which the intervention group improved relative to the comparison

group. Because agencies are randomly assigned, we expect clinicians and children in our intervention and comparison groups to be similar across baseline characteristics; however, if we find between-group differences we will control for them in our regression models.

Aim 2: Examine the cost effectiveness of Project ImPACT at different doses.

Overview

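### Aim 1 is tested on a group-by-time coefficient with six randomised agencies, but the plan states neither a by-time random effect nor a df method, so the test need not reflect clustering of change by agency

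*Combined protocol and SAP*

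**What the plan says.** All references are to the combined protocol and SAP.

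- **Cluster Randomized Study Design:** "Six agencies will be blocked into groups of 3 based on agency size and location", and within each block the three agencies go one to each arm. That gives two agencies per arm.
- **Statistical Analysis for Aim 1:** a longitudinal nested linear model with time (categorical), group and their interaction as fixed effects. On the random part: "the models will consist of three levels of random effects to adjust for individual child/parent, agency and clinician variability". On the test: "The magnitude and statistical significance of the beta coefficient for the interaction will provide an intent-to-treat assessment".
- **Not stated anywhere:** whether the random effects are intercepts only or include time, the covariance structure, the denominator df or any small-sample correction, and whether block is fitted.
- **Measures:** for child outcomes, "all measures collected at baseline and 6 months"; for parent outcomes, "All measures will be completed at baseline, 3 months, and 6 months".
- **Clinician training:** in the ImPACT arms, "clinicians will present their Project ImPACT cases to the other clinicians in their agency" at group consultation meetings. There are also "twice-a-month cross-site video-based fidelity checks to ensure that Penn staff is providing training and feedback".
- **Statistical Power:** two separate two-level calculations with an ICC of 0.05, giving 80% power at d=0.66 (clinicians within agencies) and d=0.53 (patients within clinicians).
- **Aim 2, Data Analysis:** an incremental cost-effectiveness ratio is built only for outcomes on which ImPACT shows a significant effect.

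**The concern.** Agency appears in the model, which looks like protection for a trial that randomises agencies. But the tested quantity is a difference between arms in change. An agency intercept is common to an agency's baseline and follow-up values, so it drops out of change. What would threaten the test is agencies differing in how much their families change, and only a by-time random effect or an agency-level comparison of change captures that. If such variation exists and is not modelled, tests reject too often and intervals are too narrow.

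If by-time effects are what the plan intends, a second gap matters. Six agencies less three arms leave 3 df, and a normal or child-level reference distribution would be too generous.

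The same significance result decides which outcomes enter the cost-effectiveness analysis, so a false positive in Aim 1 would carry into Aim 2.

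**Working it through.** **Inputs from the documents.** 3 arms × 2 agencies × 3 clinicians × 3 children = 54 children, so 9 per agency and 18 per arm; two-sided alpha 0.05; two visits for child outcomes and three for parent outcomes. **Assumed, because the documents give no values:** the agency ICC of change ρ (0 to 0.10), the baseline/follow-up correlation r, normal data, and total variance of change equal across arms (set to 1).

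**1. The plan's own power figures.** With 18 per arm, detectable d = (1.96 + 0.84) × √(2 × DE/18). This is 0.93 at DE = 1, 0.98 at DE = 1 + 2 × 0.05 = 1.1, and 1.10 at DE = 1 + 8 × 0.05 = 1.4. The stated 0.66 and 0.53 do not follow from the printed inputs. The software settings, such as any baseline correlation, are not reported, and nothing below depends on this.

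**2. Do the intercepts cancel?** Generalised least squares on this layout, random intercepts only, gives a standard error for the 6-month interaction of √(2/18) = 0.3333 SD of change. It is the same whether the agency and clinician variances are 0, 0.05 or 5, and for two or three visits. With 8 of 54 six-month values missing at random it moves by at most 0.9%.

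**3. Rejection rate, random intercepts only.** With ρ in all arms, the true variance of an arm contrast is (2/18)(1 + 8ρ). The residual mean square on 51 df has expectation 1 − 8ρ/17. Approximate size = P(|t₅₁| > 2.008/√[(1 + 8ρ)/(1 − 8ρ/17)]). At ρ = 0.05 the ratio is 1.4/0.9765 = 1.434, the effective cut-off is 2.008/1.197 = 1.677, and the size is 10.0%.

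If only ImPACT agencies cluster, the numerator is 1 + 4ρ for ImPACT versus usual care and 1 + 8ρ for dose versus dose, and the denominator is 1 − (2/3)(8ρ/17). Simulation of 400,000 null trials per setting gave:

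| Agency ICC of change | 0 | 0.01 | 0.02 | 0.05 | 0.10 |
|---|---|---|---|---|---|
| All arms cluster, any pair | 5.0% | 6.0% | 6.9% | 10.0% | 15.1% |
| ImPACT only: ImPACT v usual care | 5.0% | 5.5% | 6.0% | 7.5% | 10.1% |
| ImPACT only: dose v dose | 5.0% | 5.9% | 6.9% | 9.8% | 14.7% |

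The formula agrees within about 0.1 point. Three-visit outcomes agree within 0.2 points. Clustering of change by clinician alone, at 0.05 or 0.10 in all arms, gives 6.2 or 7.5%.

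**4. Rejection rate, agency variation estimated but normal reference.** P(|t₃| > 1.96) = 14.5%, whatever ρ is. This is for an unconstrained agency-mean comparison. The correct cut-off is 3.18 on 3 df, or 4.30 on 2 df if block is fitted.

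**5. Agency-mean comparison on 3 df.** Size is 5.0% at every ρ if all arms cluster. If only ImPACT agencies cluster (ρ 0.01 to 0.10), it is 4.6 to 4.9% for ImPACT versus usual care and 5.1 to 6.3% for dose versus dose, so close to nominal but not exact.

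**6. What that test costs at ρ = 0.** The 95% half-width rises from 2.008 × 0.333 = 0.67 to 3.182 × 0.333 = 1.06 SD of change. For power, SD of change = outcome SD × √(2(1 − r)) and noncentrality = d/(√(2(1 − r)) × 0.3333). At d = 0.66 in outcome SDs:

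| r | Noncentrality | 51 df | 3 df | 2 df |
|---|---|---|---|---|
| 0.5 | 1.98 | 49% | 28% | 22% |
| 0.7 | 2.56 | 71% | 42% | 31% |
| 0.8 | 3.13 | 87% | 56% | 41% |

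On 3 df, 80% is reached only at r of about 0.89. At d = 0.53, power on 3 df is 20, 30 or 41%, and 80% needs r of about 0.93.

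**The case against.** The strongest reply is that the harm is doubly conditional. The plan names agency and clinician as random effects and considers both levels of nesting in its power section, so it plainly means to respect the design, and a model with by-time effects and agency-level df would fit its wording. Inflation also needs change to cluster by agency. The evidence on that is mixed: consultation within each agency could create clustering in the ImPACT arms, while common supervision and cross-site fidelity checks would tend to reduce it. All of this stands, and it limits the point to what the text fails to secure.

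Four stronger readings are tempting but not supported:

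- *Clustering is ignored.* It is not; agency is in the model.
- *The Aim 1 test is inflated.* The documents do not show this. At an ICC of change of zero the intercept-only test holds 5%.
- *The plan's ICC of 0.05 makes the error rate 10%.* The power section does not tie that ICC to change.
- *The dose comparison is worst affected.* That is so only if the ImPACT agencies alone cluster; if all arms cluster, every pair is affected alike. The Aim 1 analysis section describes improvement relative to the comparison group and specifies no dose-versus-dose test, although Aim 1 and Aim 2 imply one.

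It is also fair to say that the remedy gives up 21 to 31 points of power at d = 0.66 if there is no clustering, against an excess error of about 1 to 5 points at ICC 0.01 to 0.05. That is a reason to show the cost openly. It does not make a test valid if change does cluster.

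**Conclusion.** The concern holds as a gap in specification with a material consequence. On the ordinary reading the named agency term does nothing for the tested coefficient. On the by-time reading the missing df method leaves the test open to about 14.5% rejection under a normal reference. Neither ordinary way of following the text secures the 5% level.

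The size on the first reading depends on an ICC of change that the documents do not give: no inflation at 0, about 6% at 0.01, 10% at 0.05 and 15% at 0.10 if all arms cluster, and less for ImPACT versus usual care if only ImPACT agencies do. These figures assume normal data and the planned 3 × 2 × 3 × 3 layout. Confidence is high on the omission and on the cancellation, and cannot be high on the amount of inflation. It should be fixed before analysis.

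**What to change.** 1. State the random-effects structure, and state that arm contrasts in change are tested at the level of the randomised agency. Either compare agency mean changes on 3 df (2 if block is fitted), or fit agency-by-time and clinician-by-time random effects with Satterthwaite or Kenward-Roger df.
2. For the model route, fix a rule for an agency-by-time variance estimated as zero: fall back on the agency-mean comparison. In a simulated model with agency-by-time alone, the estimate was zero in 60, 43 or 32% of trials at an ICC of 0, 0.05 or 0.10 in all arms. In balanced data, this fallback makes the two routes largely the same test.
3. Fix in advance whether block is fitted.
4. Report Aim 1 mainly as estimates with these intervals. That suits the study's stated role: "Findings from this pilot trial would serve as the foundation for an application for federal funds".
5. Restate the 80% power figures on the same basis, giving the assumed ICC of change and baseline/follow-up correlation.
6. Say whether cost-effectiveness ratios will also be reported, as estimates with uncertainty, regardless of significance. If the significance rule stays, the wider intervals will leave fewer outcomes for Aim 2.

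The change needs wording and model code, and no new data. Its cost is the wider intervals and lower power shown above. A randomisation test does not avoid that cost. Two blocks of three give 6 × 6 = 36 allocations, so even under a null of no effect in any arm the smallest two-sided p for a pairwise contrast is 2/36 = 0.056. No analysis choice can make up for having two agencies per arm.

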We base our statistical power analysis upon Aim 1, our primary aim, which tests the effects of Project ImPACT on child and parent outcomes. Prior studies of Project ImPACT and related parent-mediated interventions indi-cate a large effect on parent treatment adherence (.90-1.30), and a moderate effect on child outcomes (.34-.70).16,19,42 Meta-analytic reviews of studies of parent-implemented interventions for children with ASD report effects of .8 to 1.1.26 We used Power and Precision software, and assumed an alpha of 0.05, and that all tests are 2-tailed. We will have enrolled 3 clinicians in each agency and 3 children per clinician (18 subjects per intervention group). Due to statistical software limitations in addressing multiple levels of clustering in power estima-tion, we adopted two perspectives. First, we explored potential effect sizes (Cohen's d) with nesting of clinicians within agencies. Second, we estimated potential effect sizes with nesting of patients within clinicians. We as-sume an intra-class correlation of 0.05. In the first case, we calculate that we will have power of 80% to detect a moderate intervention effect of d=0.66. In the second case, we calculate that we will have power of 80% to de-tect a moderate intervention effect of d=0.53.

PROTECTION OF HUMAN SUBJECTS

Research will not begin until the Institutional Review Boards of the University of Pennsylvania and the City of Philadelphia approve the proposed study.

Characteristics of Population

We anticipate the sample of parent-child dyads will be 45% African American, 26% Latino, 18% Caucasian, 6% Asian, 2% American Indian/Native American, and 3% multi-racial. Children will be less than 3 years of age, and will either have a diagnosis of autism spectrum disorder or be identified as at-risk for autism by the early intervention system, as children under three years of age do not need a formal diagnosis to receive autism-specific treatment. We anticipate that 75% of the children will be male based on the sex distribution of autism. Participants will be excluded if they do not speak English. This is due to the procedures of the project, which include coding of videos of early intervention sessions. The team currently does not have capacity to code videos that are not in English. Participants will not be excluded based on their gender or past experience.

Data to be collected from Human Subjects

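### Aim 1 tests a group-by-time interaction with baseline as an outcome and does not prespecify adjustment for the baseline score; this probably costs precision, by an amount that depends on assumptions the documents do not settle

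*Combined protocol and SAP*

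**What the plan says.** Statistical Analysis for Aim 1 states: "The dependent variable in each model will be the measure of outcome at each time point". On the model terms: "The independent variables will include a categorical variable for time period (baseline, 3 months, or 6 months), group", and the interaction of the two. The model has "three levels of random effects to adjust for individual child/parent, agency and clinician variability". The test is defined by this sentence: "The magnitude and statistical significance of the beta coefficient for the interaction will provide an intent-to-treat assessment".

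Baseline is therefore a response with its own free mean in each arm. It is not a covariate. The only provision for adjustment is conditional: "if we find between-group differences we will control for them in our regression models". That sentence does not name the baseline outcome.

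Under Measures, the note for child outcomes is "all measures collected at baseline and 6 months", and for parent outcomes it is "All measures will be completed at baseline, 3 months, and 6 months". The baseline scores needed for adjustment are thus already collected. Statistical Power gives 18 children per arm and an intra-class correlation of 0.05. It mentions neither a baseline-to-follow-up correlation nor any gain from using baseline.

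**The concern.** With two time points and complete data, the interaction is the difference between arms in mean change from baseline. A change score subtracts the whole baseline value, including its noise. A covariate model subtracts only the part of baseline that predicts follow-up. In a trial with independent participants and r below 1, the second is more precise.

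The conditional clause does not close the gap. The gain comes from the correlation of baseline with outcome, not from observed imbalance, and a rule triggered by looking at the data leaves the primary model undefined in advance.

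The trial has 18 children per arm in six agencies, so precision is scarce and a gain that needs no extra data is worth having. The question is how much of the textbook gain survives clustering.

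**Working it through.** **Plan's own figure.** There is none on this point. The nearest are the detectable effects of 0.66 and 0.53 in Statistical Power, which refer to no baseline adjustment. They do not follow from 18 per arm: 2.80 × √(2/18) = 0.93 with no clustering, and 2.80 × √(2 × 1.10/18) = 0.98 with three children per clinician. That is a separate problem and is not used below.

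**Inputs from the documents.** Two agencies per arm, three clinicians per agency and three children per clinician, so 9 children per agency and 18 per arm. Intra-class correlation 0.05, here applied to the agency.

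**Assumptions.** r = 0.4, 0.6 and 0.8; variance 1 at each time point; complete data. Agency variance a is split into a stable part a_s and a time-specific part a_t. The stable child variance is s = r − a_s, the residual is e = 1 − r − a_t, and the child-level baseline slope is b = s/(s + e).

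**Independent children (a = 0).** The variance of the arm difference is proportional to 2(1 − r) for change and 1 − r² for baseline adjustment. The ratio of adjusted to change is (1 + r)/2, so the share lost is (1 − r)/2: 30%, 20%, 10%. Eighteen per arm works like 12.6, 14.4, 16.2.

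**With agency effects.**

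- Change: V = 2 × [2a_t/2 + 2e/18].
- Baseline-adjusted: V = 2 × {[(1 − b)²a_s + (1 + b²)a_t]/2 + [(1 − b)²s + (1 + b²)e]/18}.

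Stable agency effects cancel from the change. In the adjusted analysis a fraction (1 − b) of each remains, which is why the gain shrinks.

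Example with a = 0.05, all stable, r = 0.4: s = 0.35, e = 0.60, b = 0.35/0.95 = 0.368. Change: 2 × 1.20/18 = 0.1333. Adjusted: 0.1112. Loss: 1 − 0.1112/0.1333 = 17%.

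Example with a = 0.05, half time-specific, r = 0.4: s = 0.375, e = 0.575, b = 0.395. Change: 2 × (0.025 + 1.15/18) = 0.1778. Adjusted: 0.1272. Loss: 28%.

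| Agency correlation | r = 0.4 | r = 0.6 | r = 0.8 |
|---|---|---|---|
| 0 (independent children) | 30% | 20% | 10% |
| 0.05, stable | 17% | 11% | 5.5% |
| 0.05, stable, plus clinician 0.05 | 11% | 7% | 4% |
| 0.05, half time-specific | 28% | 21% | 12.5% |
| 0.10, stable | 0% | 0% | 0% |
| 0.15, stable | −21% | −14% | −7% |

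Entries are the share of effective sample lost by the planned analysis. A negative entry gives the extra variance of baseline adjustment, so there the planned analysis is the more precise.

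**Parent outcomes.** For the 6-month contrast of independent parents the loss is the same (1 − r)/2. If the effect were averaged over 3 and 6 months, with equal correlations and no clustering, it would be 2(1 − r)/3, or 40% to 13%. The plan does not say which interaction coefficient is primary.

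**The case against.** The strongest case for the plan has four parts.

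**Clustering.** Six agencies are randomized, and the planned random intercepts remove stable agency and clinician effects from the change. A reader might infer that the interaction always loses, and that 10% to 30% is a property of this trial. The documents do not support that. They give no r, the range needs independent children, and at a stable agency correlation of 0.10 the gain is gone. This part stands and limits the size.

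**Degrees of freedom.** A group effect on one follow-up score per child is a between-agency contrast with about 6 − 3 = 3 degrees of freedom (t = 3.18). The planned interaction is treated as a within-child contrast with about 51 (t = 2.01). On that basis, at a stable 0.05, the adjusted interval is 1.45 to 1.54 times as wide: √0.834 × 3.18/2.01 to √0.945 × 3.18/2.01. But the 51 are valid only if agency effects are constant over six months. If half of an agency variance of 0.05 is time-specific, simulated type I error of the planned test is roughly 10% to 18%. With agency-level degrees of freedom for both analyses, baseline adjustment has equal or higher power at 0.05. The shortage of degrees of freedom is real, but it does not favour the interaction.

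**Recruitment after allocation.** Consent Process has clinicians learn their arm and then refer families. A reader might infer that a baseline covariate is immune because it does not force baseline means to be equal. It is not. If the arms truly differ at baseline by D in stable characteristics, adjustment removes b × D and leaves (1 − b) × D. For an illustrative D of 0.3 SD and r of 0.4 to 0.6 with independent children, 0.18 to 0.12 SD remains. The change comparison removes all of D if the arms would have run in parallel, but is exposed to regression to the mean if they would not. This part stands and is the reason to report both analyses.

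**Baseline is already used.** A reader might infer that the plan discards baseline or is biased. Neither is so: baseline enters as a response, and the planned model is a conventional one.

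**Conclusion.** The point holds as an efficiency recommendation of moderate weight. The plan tests a comparison of change and leaves adjustment for the baseline score unspecified. At the only intra-class correlation the protocol states, applied to the agency, the planned analysis is less precise at every r examined: by 17% to 5% if agency effects are stable and 28% to 12% if half their variance is time-specific. Eighteen children per arm then work like about 15 to 17, or about 13 to 16.

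These figures rest on the assumed r of 0.4 to 0.8, on complete data, and on placing the 0.05 at agency level; adding the same value for clinicians lowers the stable-effects loss to 11% to 4%. The documents do not support a universal claim that baseline adjustment is more precise here, or that it removes differences introduced by referral after allocation.

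**What to change.** Prespecify as the main analysis, for each outcome, a mixed model of the follow-up score (6 months for child outcomes; 3 and 6 months for parent outcomes), with:

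- the baseline score as a covariate, whatever imbalance is observed;
- group as the tested effect, naming the primary time point for parent outcomes;
- agency and clinician random effects kept, plus a child/parent effect where there are two follow-ups;
- small-sample degrees of freedom that reflect six agencies.

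Keep the group-by-time interaction model as a sensitivity analysis and report the two side by side.

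The cost is SAP wording and a little programming. Three downsides should be stated in the plan. Families with only a baseline value leave the child-outcome model. Agency-level degrees of freedom are few, about 3. Baseline adjustment removes only part of any true baseline difference that arises from referral after allocation.
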